## 6. STATISTICAL ANALYSES

### 6.1. Patient Disposition

Patient disposition will be summarized for Combined Double-Blind and Open-label Period for the 2 treatment groups described in Section 5.1 for all patients enrolled, and will include the frequency count and percentage for the following categories: patients who enrolled into the study (double-blind treatment period), patients randomized, patients who entered the OLE period of the study, patients who completed the study, patients who are ongoing in the study (if applicable), and patients who discontinued early. The reasons for discontinuation will also be summarized. Descriptive statistics will be presented for duration of study (weeks).

Patient disposition and patient eligibility will be presented in data listings.

### 6.2. Demographics and Baseline Characteristics

Demographic and baseline characteristics will be summarized by Analysis Period and treatment groups described in Section 5.1 for the Safety Analysis Set. Demographics and baseline characteristics will be presented for the double-blind treatment period as well as the casimersen period. These variables will include age (years), race, ethnicity, Baseline ulnar length (cm), Baseline calculated height (cm), Baseline weight (kg), Baseline body mass index (BMI; kg/m^2), time since DMD diagnosis (months) to Baseline, corticosteroid type (Deflazacort or Prednisone), corticosteroid frequency (continuous versus intermittent), mutation type(s), duration of prior corticosteroid treatment (months) at Baseline, and Baseline 6MWT distance (m), and ambulatory status at Baseline. Additional baseline variables may be included.

Patient-level demographic data and baseline characteristics will be presented in a data listing.

### 6.3. Prior and Concomitant Medications

Concomitant medications will be coded by preferred term using the most recent World Health Organization (WHO) Drug Dictionary (WHODRUG, 01DEC2013). The number and percentage of subjects in the safety population taking concomitant medications will be tabulated by Anatomical Therapeutic Chemical (ATC) classification pharmacological subgroup and WHO drug preferred term by period and treatment groups described in Section 5.1. For the summary of the double-blind period, only dose levels of  $\leq 20$  mg/kg and 30 mg/kg will be presented for casimersen as well as total casimersen. At each level of summarization, a patient is counted once if he reported 1 or more medications at that level.

All medications, whether prior or concomitant, will be presented in data listings. Separate listings of glucocorticoids and prior experimental DMD drugs will be provided.

### 6.4. Medical History

Medical history data for the safety set will be presented in data listings.

## **6.5. Physiotherapeutic Interventions**

A listing of all physiotherapeutic interventions will be provided.

## **6.6. Protocol Deviations**

A listing of major protocol deviations will be provided. The major protocol deviations will be identified based on a review of the study data prior to the database lock and will include the nature of the deviation (eg, inclusion/exclusion, prohibited therapies).

## **6.7. Exposure to Study Drug**

The exposure to casimersen and placebo will be summarized by Analysis period and treatment groups described in Section 5.1 for the Safety Analysis Set. For the double-blind period analysis, summaries for individual dose levels will not be presented. Only the overall casimersen exposure will be described. The variables will include the following (as applicable): cumulative amount of drug received administered (mg), total number of infusions received, number of infusions of casimersen at 30 mg/kg, duration on casimersen or placebo (weeks), and patient years. Additionally, for the summary of Combined Double-blind and Open-label Periods exposure, duration on casimersen category will be summarized for the following intervals: < 24 Weeks, 24 to < 48 Weeks, 48 to < 72 Weeks, 72 to < 96 Weeks, 96 to < 120 Weeks, and  $\geq$  120 Weeks.

Patient-level dosing information will be provided in a data listing.

## **6.8. Safety Analyses**

Safety analyses by Analysis period and treatment groups described in Section 5.1 (double-blind period and casimersen period) will include summaries of the following:

- the type, frequency, severity, timing, and relationship to the study drug of AEs, SAEs, and discontinuations due to AEs. Adverse events will be coded using the Medical Dictionary for Regulatory Activities (MedDRA 17.1 and will be reported by primary system organ class (SOC) and preferred term (PT)).
- safety laboratory testing including hematology, coagulation, serum chemistry, and urinalysis
- vital signs
- physical examinations
- 12-lead ECGs
- ECHOs

### **6.8.1. Adverse Events**

In general, only TEAEs will be summarized. Nontreatment-emergent events will be recorded in the data listings. For all AE tables, the number and percentage of patients reporting AEs will be grouped using the MedDRA SOC and PT and summarized by Analysis period and, the treatment group as described in Section 5.1, and by dose level for the Double-Blind Period summary.

An overall summary table of TEAEs will be produced and will include the frequency and percentage of patients with TEAEs, treatment-related TEAEs, severe TEAEs, nonserious AEs, SAEs, treatment-related SAEs, AEs leading to discontinuation of study drug, the number of events at each severity level (mild, moderate, or severe).

Multiple occurrences of the same AE (at the preferred term level) in the same patient will be counted only once in the frequency tables. If a patient experiences multiple episodes of the same event with a different relationship/severity, the event with the strongest relationship or maximum severity to the study drug product will be used to summarize AEs by relationship and severity.

The following summary tables will be produced:

- TEAEs by SOC and PT
- TEAEs by SOC, PT, and severity
- TEAEs by descending frequency of PT
- treatment-related TEAEs by SOC and PT
- treatment-related TEAEs by SOC, PT, and severity
- treatment-related TEAEs by descending frequency of PT
- treatment-emergent nonserious AEs
- treatment-emergent SAEs
- treatment-related, treatment-emergent SAEs

The following listings will be produced:

- all AEs
- AEs leading to discontinuation
- all SAEs

### **6.8.2. Deaths**

A summary of deaths and reasons for deaths will be presented by Analysis period and treatment group. A patient-level listing will be provided. Adverse Events of Special Interest

TEAEs of special interest will be summarized by SOC and PT for each Analysis Period and treatment group as defined in Section 5.1 and by dose level for the Double-Blind summary. All standard MedDRA queries ([SMQs] based on MedDRA Version 17.1) listed below will include broad and narrow terms. The AEs of special interest (AESI) are:

- infusion-related reaction (IRR) (AEs occurring within 24 hours of the start of any infusion [including events occurring on the same date as an infusion where infusion start time or AE onset time was not reported])
- hypersensitivity (hypersensitivity SMQ)
- renal toxicity (acute renal failure SMQ)

Summaries of adjudicated-IRRs will also be generated. Adjudicated IRRs will be identified by Pharmacovigilance review of all IRRs as defined above.

An overall summary of AESI events will include total number of events, number of serious events, number of treatment-related events, number of unrelated events, number of mild events, number of moderate events, number of severe events, and number of events occurring on the same day as an infusion (within 24 hours or on the same day with no time). A listing of each AESI strategy and a listing of AEs related to study drug for each AESI strategy will be generated.

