- ^g Before patients may begin dosing in the open-label extension period, safety laboratory assessments must be performed within 2 weeks prior to first dose. If safety laboratory samples were collected more than 2 weeks prior to the first open-label extension visit, samples must be collected again and results must be reviewed before dosing.
- ^h At Weeks 24, 36, 48, 72, 84, 96, 108, and 120. CCI [REDACTED] Additional samples will also be taken at Weeks 24, 48, 72, 96, and 120 approximately 2-4 hours after completion of the infusion. At Week 60, plasma samples for serial PK will be obtained immediately pre-infusion, approximately 5 to 10 minutes after completion of the infusion, and approximately 1, 1.5, 2, 4, 6, 8, 12, 16, and 24 hours after completion of the infusion.
- ⁱ All patients will receive open-label treatment with SRP-4045 at 30 mg/kg (or the highest tolerated dose as determined during the dose titration) administered weekly. Infusions are to be given according to instructions in the Pharmacy Manual. Note that an implanted venous access port may be inserted for treatment administration at the discretion of the Investigator. Patients are to be closely monitored for at least 1 hour following the completion of all infusions. If the patient has not experienced an infusion reaction after 48 weeks of open-label treatment, the Investigator has discretion to reduce the post-infusion observation period to 30 minutes.
- ^j Home infusions may take place 3 out of every 4 weeks, with the fourth week conducted at the study site. This schedule is intended to reduce study burden while maintaining ongoing in-person surveillance by the study site. Detailed instructions for in-home dosing will be provided in a separate manual to the visiting nurse.

Table 2: Schedule of Events: Double-Blind Dose Titration with Open-Label Extension, continued

Week	121-131	132	133-143	144	F/U EoS/ ET ^a
Visit Window	After transition to open-label SRP-4045: ±3 days such that no 2 infusions are less than 60 hours apart				
CCI					
12-lead ECG		X		X	
ECHO		X			
Full Physical Exam ^c				X	X
Brief Physical Examination ^d		X			
Height and ulnar length ^e		X		X	X
Weight	Once every 4 weeks				X
Vital signs ^f	Weekly Pre- and Post-Infusion				X
Safety Lab Assessments ^g		X		X	X
CCI					
Dosing ^h	Weekly Infusions: Patients to receive placebo or SRP-4045 as randomized until DSMB review and Sponsor determination of weekly open-label dose level				
Concomitant medications	Continuous				

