11.4. Recording Adverse Events

All AEs experienced from the time of informed consent/assent to the last follow-up (ie, 4 weeks after the last dose of investigational drug product) will be recorded within each patient's eCRF. Information should include: a concise description of the event; date and time of event onset and resolution; determination of seriousness, severity, corrective treatment, outcome, and relationship to investigational product or study procedure or underlying disease; and any action taken will be recorded. Resolution occurs when the patient has returned to his baseline state of health or further improvement or worsening of the event is not expected.

Whenever possible, a diagnosis will be recorded as an AE, rather than symptoms or isolated laboratory abnormalities related to that diagnosis. Several symptoms or laboratory results that are related to the same diagnosis can thus be part of the same AE.

A medical or surgical procedure is not an AE; rather the condition leading to the procedure should be recorded as the AE. Similarly, death is not an AE, but is rather the outcome of the AE(s) that resulted in death. If the AE(s) leading to death are not known, then death must be reported as an AE. All AEs will be followed until the resolution of AE, completion of the patient's study participation, or study termination, whichever occurs first. Serious AEs will be followed until resolution or until the condition stabilizes or returns to baseline status or until no further follow-up is expected.

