### 5.2.2. Imputation of Missing Values

Missing laboratory values will be imputed as described in section 5.2.1. Missing dates will be imputed as described in section 5.2.3. If a patient had missing data for any other reason, values will not be imputed.

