### 5.2.3. Handling of Incomplete Dates

An incomplete date will occur when the exact date an event occurred or ended cannot be obtained for a patient. Incomplete dates will be imputed as follows:

- For a partial or missing medication date, the medication will be classified as a concomitant medication unless the available part of the date indicates it is impossible for the drug to be concomitant. For example, if only the year for the stop date is available and the year is prior to the year of dosing, the medication will be classified as a prior medication.
- For a partial or missing adverse event (AE) onset date, the event will be classified as treatment-emergent if the month and/or year of the onset date are on or after the initiation of treatment (casimersen or placebo, as appropriate)
- For calculating the time since DMD diagnosis or duration of prior corticosteroid use, if the date of DMD diagnosis or the start date of corticosteroid use has a missing day, but known month and year, then the 15th of the month will be used in the calculation. If the date has a missing day and month and only the year is known, December 31st of the recorded year will be used in the calculation.

In all cases, the original missing or incomplete dates will be presented in the data listings.

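### When a clock time is missing, the infusion-related-reaction rule stops at midnight although its window is 24 hours, so some possible reactions never reach adjudication

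*SAP*

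**What the plan says.** The rule is in the adverse-events-of-special-interest text of SAP 6.8.2 (the section headed Deaths). An IRR covers "AEs occurring within 24 hours of the start of any infusion". A bracket extends it to events with an unknown time: "including events occurring on the same date as an infusion where infusion start time or AE onset time was not reported". The overall summary of events of special interest uses the same fallback: "number of events occurring on the same day as an infusion (within 24 hours or on the same day with no time". SAP 6.8.3 repeats that line for the additional events for review.

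Adjudication starts from the flagged set: "Adjudicated IRRs will be identified by Pharmacovigilance review of all IRRs as defined above".

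The missing-data rules supply no clock time. SAP 5.2.2 refers to the laboratory and date rules and then says "If a patient had missing data for any other reason, values will not be imputed". SAP 5.2.3 deals with incomplete onset dates, and only to decide treatment emergence: "For a partial or missing adverse event (AE) onset date, the event will be classified as treatment-emergent".

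Protocol 11.4 asks sites to record "date and time of event onset and resolution", so an onset time is expected for every event.

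**The concern.** A 24-hour window opened by a daytime infusion always runs into the next calendar date. The fallback covers only the infusion's own date. An event the following morning is therefore an IRR if both times were recorded, and is not if either is absent. The missing clock time alone changes the classification.

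Adjudication cannot repair this. Pharmacovigilance can remove a flagged event that is not a reaction, but it never sees an event that was not flagged. What is at stake is the adjudicated IRR summary for one of the three events of special interest, and in particular reactions that begin overnight or the next morning. Protocol 9.6 requires observation for at least 1 hour after an infusion, reducible to 30 minutes after 48 weeks of open-label treatment without a reaction. Later onset times may therefore rest on patient or caregiver report.

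**Working it through.** The plan states no figure to reproduce. The check has three steps.

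**1. The rule applied to single records.** Take an infusion at 10:00 (assumed). With both times known, an event is an IRR if onset minus start lies between 0 and 24 hours. With either time missing, it is an IRR only if it falls on the infusion date.

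| Event | Infusion time | Onset time | Result |
|---|---|---|---|
| Next date, 04:00 | known | known | IRR (18 h) |
| Next date | known | missing | not IRR |
| Next date, 04:00 | missing | known | not IRR |
| Same date, 04:00 | known | known | not IRR (6 h before the infusion) |
| Same date, 04:00 | missing | known | IRR |
| Same date | known | missing | IRR |

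Rows 2 and 3 are possible omissions. Row 3 is notable: any infusion start at or after 04:00 would put that event inside the window. Rows 5 and 6 show the opposite error, because the fallback can accept an event that came before the infusion.

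**2. Clock time on each side.** For a start at clock hour h, the window covers 24 − h hours of the infusion date and h hours of the next date. The next-date share is h/24. The documents give no start times; 09:00 to 15:00 is assumed.

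- 09:00: 9/24 = 37.5%
- 11:00: 11/24 = 45.8%
- 13:00: 13/24 = 54.2%
- 15:00: 15/24 = 62.5%

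The fallback also accepts the h hours of the infusion date before the start. With an 11:00 start, 11 in-window hours are lost and 11 pre-infusion hours are gained. If untimed events arise at a constant background rate, the two cancel in the unadjudicated count.

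**3. Share of in-window events missed.** Clock time equals event share only if onset is uniform over the window. For exponential onset with mean m hours, truncated at 24 hours, the missed share is [F(24) − F(24 − h)]/F(24), with F(t) = 1 − exp(−t/m).

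For m = 6, F(24) = 1 − exp(−4) = 0.9817.

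- h = 9: F(15) = 1 − exp(−2.5) = 0.9179, so (0.9817 − 0.9179)/0.9817 = 6.5%.
- h = 15: F(9) = 1 − exp(−1.5) = 0.7769, so (0.9817 − 0.7769)/0.9817 = 20.9%.

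| Assumed onset | 09:00 start | 15:00 start |
|---|---|---|
| Uniform over 24 h | 37.5% | 62.5% |
| Exponential, mean 24 h | 26.5% | 50.5% |
| Exponential, mean 12 h | 17.5% | 39.0% |
| Exponential, mean 6 h | 6.5% | 20.9% |

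These are shares of in-window events with a missing time, not of all IRRs. The effect on the total is the table entry multiplied by the fraction of in-window events lacking a time, which the documents do not give.

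**The case against.** The strongest objection is to a reading that the rule invites: that all IRR counts are biased downward by 38% to 63%. The documents do not support that. The fallback errs in both directions, and after the first infusion an event that starts before a later weekly infusion is already treatment-emergent under SAP 5.8, so it can enter the count. A net loss in the unadjudicated count requires onset to cluster after the infusion, and clustering is exactly what reduces the missed share. This objection stands. It does not reach the adjudicated count, where review can take out the pre-infusion events but cannot restore the missed ones.

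Missing times should also be uncommon. Onset time is a required item (Protocol 11.4), source data verification is 100% (Protocol 13.1), and missing data are checked and queried (Protocol 13.2). This stands as a limit on size. The SAP's own fallback, however, shows that some missing times are anticipated.

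A reader might infer that the loss falls mainly on home infusions. The protocol says only "Home infusions may take place 3 out of every 4 weeks, with the fourth week conducted at the study site", and Protocol 9.6 mentions home dosing only for the open-label extension. Nothing shows that times are more often missing there. In the serial sampling weeks, a 24-hour sample also brings next-day contact (Protocol 10.5.1).

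Finally, no event disappears from the safety report. It remains in the treatment-emergent tables and the listing of all events (SAP 6.8.1), and may enter the hypersensitivity grouping. IRR is also not named in the primary endpoint (Protocol 7.3). Both points are correct and keep this a minor matter.

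**Conclusion.** The point holds for adjudicated IRRs. The fallback does not match the 24-hour definition, nothing elsewhere in the SAP supplies a clock time, and adjudication is closed to events that were not flagged. The text does not exclude next-date events in so many words; that follows from the same-date bracket together with the no-imputation rule. The direction of error in the unadjudicated count is not established.

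Among in-window events with a missing time, about 6.5% to 21% would be missed with front-loaded onset of mean 6 hours, rising to 38% to 63% only if onset is uniform. Start times and onset distributions are assumptions. The absolute effect depends on an unknown, probably small, number of missing times, and could be zero in 12 patients. In the double-blind period, one affected patient with no other IRR would move the percentage by 1/8 = 12.5 points on casimersen or 1/4 = 25 points on placebo. The amendment is inexpensive and worth making, but the defect is not a serious one.

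**What to change.** Add to SAP 6.8.2, after the sentence on adjudicated IRRs: 'Pharmacovigilance will also review any AE with onset on the calendar date after an infusion where the infusion start time or AE onset time is missing and the available data do not rule out onset within 24 hours of the infusion start. These events will be flagged as timing not determinable. Those judged to be IRRs will be counted in the adjudicated-IRR summary. The unadjudicated IRR count will be shown with and without the flagged events.'

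Keep these events out of the main unadjudicated count. Adding them all would stretch a 24-hour window over two calendar dates for untimed events and leave the pre-infusion inclusions in place. Do not extend the rule to SAP 6.8.3, where no adjudication is planned to remove the extra events.

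The change should be made before the final database lock, while the double-blind assignment is still masked (SAP 4.3.2). The cost is a short SAP amendment, a small programming change, a few extra events to adjudicate and one extra count.

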#### **6.8.3. Additional AE for Review**

Additional TEAEs for review will be summarized by SOC and PT for each Analysis Period and treatment group as defined in Section 5.1 and by dose level for the double-blind period summary. All standard MedDRA queries ([SMQs] based on MedDRA Version 17.1) listed below will include broad and narrow terms. The AEs for additional review are:

- •infusion site reaction (extravasation events SMQ and the following PTs: application site erythema, application site rash, catheter site hematoma, catheter site hemorrhage, catheter site-related reaction, infusion site rash, infusion site swelling)
- •leukopenia and neutropenia (haematopoietic leukopenia SMQ)
- •severe cutaneous adverse reactions (severe cutaneous adverse reactions SMQ)
- •drug-induced hepatotoxicities (cholestasis and jaundice of hepatic origin SMQ, hepatic failure, fibrosis, cirrhosis and other liver damage-related conditions SMQ, hepatitis, non-infectious SMQ, liver neoplasms, benign [including cysts and polyps] SMQ, liver malignant tumors SMQ, liver tumors of unspecified malignancy SMQ, liver related investigations, signs and symptoms SMQ, liver-related coagulation and bleeding disturbances SMQ)
- •cardiac events (cardiomyopathy SMQ, cardiac failure SMQ, and arrhythmia related investigations, sign and symptoms SMQ)
- •coagulopathy (haemorrhage terms [excluding lab terms] SMQ, haematopoietic thrombocytopenia SMQ, PTs in the embolism and thrombosis High Level Group Terms [HLGT])

An overall summary of additional AE for review will include total number of events, number of serious events, number of treatment-related events, number of unrelated events, number of mild events, number of moderate events, number of severe events, and number of events occurring on the same day as an infusion (within 24 hours or on the same day with no time).

A listing of each AE for additional review strategy and a listing of AEs related to study drug for each AE for additional review strategy will be generated.

